### **4.3 Benefit/Risk**

Subjects in clinical trials generally cannot expect to receive direct benefit from treatment during participation, as clinical trials are designed to provide information about the safety and effectiveness of an investigational medicine.

Additional details regarding specific benefits and risks for subjects participating in this clinical trial may be found in the accompanying Investigators Brochure (IB) and Informed Consent documents.

Beneficial effects of pembrolizumab have been seen in several trials to date. Publications of a significantly positive benefit/risk ratio have been reported for melanoma both in a single arm study encompassing nearly 1000 subjects (KN001), which led to USFDA approval in September 2014, and in a randomized comparison to chemotherapy (KEYNOTE-002 [KN002]— detailed in the IB). Additional potential benefits are addressed in section 4.1.3.1

which details responses of KN012 trial; a multi-cohort Phase Ib study of which one cohort enrolled subjects with recurrent or metastatic gastric or GEJ adenocarcinoma that expressed PD-L1 ( $\geq 1\%$  by immunohistochemistry). Although two-thirds of subjects had received at least two prior therapies for advanced disease, pembrolizumab monotherapy achieved an interim ORR of 33.3% by RECIST v.1.1 per investigator review (95% confidence interval (CI) (19.1%, 50.2%); all partial responses). The interim disease control rate (DCR) was 41% (95% CI (25.6%, 57.9%)), and the interim median duration of response was 24 weeks (range 8+ to 33+ weeks).

In KN012 the most common AEs included fatigue (17.9%), decreased appetite (12.8%), hypothyroidism (12.8%), and arthralgia (10.3%). Three Grade 3 AEs were observed, one each for peripheral sensory neuropathy, fatigue, and decreased appetite. In addition, one Grade 4 pneumonitis and one Grade 5 hypoxia were reported.

An early safety analysis will be performed to evaluate the safety of each treatment arm. This interim safety analysis will occur when at least 10 subjects from each arm (30 total subjects) have completed at least 1 cycle of treatment. The safety data will be submitted to an external DMC.

## **5.0 METHODOLOGY**

### **5.1 Entry Criteria**

#### **5.1.1 Diagnosis/Condition for Entry into the Trial**

Male/Female subjects with locally advanced unresectable or metastatic gastric or GEJ adenocarcinoma of at least 18 years of age will be enrolled in this trial.

#### **5.1.2 Subject Inclusion Criteria**

In order to be eligible for participation in this trial, the subject must:

1. Be willing and able to provide written informed consent/assent for the trial. The subject may also provide consent/assent for Future Biomedical Research. However, the subject may participate in the main trial without participating in Future Biomedical Research.
2. Be  $\geq 18$  years of age on day of signing informed consent (or acceptable age according to local regulations, whichever is older).
3. Have a performance status of 0 or 1 on the Eastern Cooperative Oncology Group (ECOG) Performance Scale within 3 days prior to the first dose of trial treatment.
4. Have histologically or cytologically confirmed diagnosis of locally advanced unresectable or metastatic gastric or GEJ adenocarcinoma.
5. Be HER2/neu negative and PD-L1 positive.

6. Have measurable disease as defined by RECIST 1.1 as determined by investigator assessment. Tumour lesions situated in a previously irradiated area are considered measurable if progression has been demonstrated in such lesions.
  - a. Note: The exact same image acquisition and processing parameters should be used throughout the study.
7. Have provided tumour tissue sample deemed adequate for PD-L1 biomarker analysis. Refer to Section 7.1.1.2.1 for details
  - a. Notification of eligibility must be received prior to randomization.
  - b. Additional samples may be required if adequate tissue is not provided.
8. Female subjects of childbearing potential must have a negative urine or serum pregnancy test within 72 hours prior to receiving the first dose of study medication. If the urine test is positive or cannot be confirmed as negative, a serum pregnancy test will be required.
9. Female subjects of childbearing potential (Section 5.7.2) must be willing to use an adequate method of contraception as outlined in Section 5.7.2 – Contraception, for the course of the study through 120 days after the last dose of study medication.

Note: Abstinence is acceptable if this is the usual lifestyle and preferred contraception for the subject.
10. Male subjects of childbearing potential (Section 5.7.2) must agree to use an adequate method of contraception as outlined in Section 5.7.2- Contraception, starting with the first dose of study therapy through 120 days after the last dose of study therapy.

Note: Abstinence is acceptable if this is the usual lifestyle and preferred contraception for the subject.
11. Demonstrate adequate organ function as defined in [Table 2](#). All screening labs should be performed within 10 days of treatment initiation.

Table 2 Adequate Organ Function Laboratory Values

System	Laboratory Value
Haematological	
Absolute neutrophil count (ANC)	≥1,500 /mcL
Platelets	≥100,000 / mcL
Haemoglobin	≥9 g/dL – transfusion is acceptable if necessary to increase haemoglobin levels
Renal	
Creatinine OR Measured or calculated a creatinine clearance  (GFR can also be used in place of creatinine or CrCl)	≤1.5 X upper limit of normal (ULN) OR ≥60 mL/min for subject with creatinine levels > 1.5 X institutional ULN Cisplatin product label should be followed for acceptable creatinine clearance rates for subjects in Arms 2 and 3 (combination treatment)
Hepatic	
Total bilirubin	≤ 1.5 X ULN OR Direct bilirubin ≤ ULN for subjects with total bilirubin levels > 1.5 ULN
AST (SGOT) and ALT (SGPT)	≤ 2.5 X ULN OR ≤ 5 X ULN for subjects with liver metastases
Albumin	≥ 2.5 g/dL
Coagulation	
International Normalized Ratio (INR) or Prothrombin Time (PT) Activated Partial Thromboplastin Time (aPTT)	≤1.5 X ULN unless subject is receiving anticoagulant therapy as long as PT or PTT is within therapeutic range of intended use of anticoagulants ≤1.5 X ULN unless subject is receiving anticoagulant therapy as long as PT or PTT is within therapeutic range of intended use of anticoagulants
a Creatinine clearance should be calculated per institutional standard.	

### 5.1.3 Subject Exclusion Criteria

The subject must be excluded from participating in the trial if the subject:

1. Has squamous cell or undifferentiated gastric cancer.
2. Has had previous therapy for locally advanced, unresectable or metastatic gastric/GEJ cancer. Subjects may have received prior neoadjuvant or adjuvant therapy as long as it was completed at least 6 months prior to randomization.

3. Has had major surgery, open biopsy or significant traumatic injury within 28 days prior to randomization, or anticipation of the need for major surgery during the course of study treatment.
4. Has had radiotherapy within 14 days of randomization. Subjects who received radiotherapy >14 days prior to randomization must have completely recovered from any radiotherapy related AEs/toxicities.
5. Has a known additional malignancy that is progressing or requires active treatment. Exceptions include basal cell carcinoma of the skin, squamous cell carcinoma of the skin that has undergone potentially curative therapy or in situ cervical cancer.
6. Has known active central nervous system (CNS) metastases and/or carcinomatous meningitis. Subjects with previously treated brain metastases may participate provided they are stable (without evidence of progression by imaging at least four weeks prior to the first dose of trial treatment and neurologic symptoms have returned to baseline), have no evidence of new or enlarging brain metastases, and are not using steroids for at least 7 days prior to trial treatment. This exception does not include carcinomatous meningitis which is excluded regardless of clinical stability.
7. Has an active autoimmune disease that has required systemic treatment in past 2 years (ie with use of disease modifying agents, corticosteroids or immunosuppressive drugs). Replacement therapy (eg, thyroxine, insulin, or physiologic corticosteroid replacement therapy for adrenal or pituitary insufficiency, etc.) is not considered a form of systemic treatment.
8. Has a diagnosis of immunodeficiency or is receiving chronic systemic steroid therapy (in dosing exceeding 10 mg daily of prednisone equivalent) or any other form of immunosuppressive therapy within 7 days prior the first dose of trial drug.
9. Has a history of (non-infectious) pneumonitis that required steroids or current pneumonitis
10. Has an active infection requiring systemic therapy.
11. Has a history or current evidence of any condition (eg known deficiency of the enzyme dihydropyrimidine dehydrogenase [DPD]), therapy, or laboratory abnormality that might confound the results of the trial, interfere with the subject's participation for the full duration of the trial, or is not in the best interest of the subject to participate, in the opinion of the treating investigator.
12. Has known psychiatric or substance abuse disorders that would interfere with cooperation with the requirements of the trial.
13. Is pregnant or breastfeeding, or expecting to conceive or father children within the projected duration of the trial, starting with the screening visit through 120 days after the last dose of trial treatment.

14. Has received prior therapy with an anti-PD-1, anti-PD-L1, or anti-PD-L2 agent.
15. Has a known history of Human Immunodeficiency Virus (HIV) (HIV 1/2 antibodies).
16. Has known active Hepatitis B (eg, HBsAg reactive) or Hepatitis C (eg, HCV RNA [qualitative] is detected).
17. Is currently participating in and receiving study therapy or has participated in a trial of an investigational agent or has used an investigational device within 4 weeks prior to the first dose of trial treatment.
18. Has received a live vaccine within 30 days prior to the first dose of trial drug.

Note: Examples of live vaccines include, but are not limited to, the following: measles, mumps, rubella, varicella/zoster (chicken pox), yellow fever, rabies, Bacillus Calmette-Guérin (BCG), and typhoid vaccine. Seasonal influenza vaccines for injection are generally killed virus vaccines and are allowed; however intranasal influenza vaccines (eg, FluMist®) are live attenuated vaccines, and are not allowed.

## **5.2 Trial Treatment(s)**

The treatments to be used in this trial are outlined below in [Table 3](#).

**Table 3 Trial Treatments**

Drug	Dose	Dose Frequency	Route of Administration	Regimen/Treatment Period/Vaccination Regimen	Use
Pembrolizumab	200 mg	Q3W	IV infusion	Day 1 of each cycle	Experimental
Normal Saline	NA	Q3W	IV infusion	Day 1 of each cycle	Placebo
Cisplatin*	80 mg/m 	Q3W	IV infusion	Day 1 of each cycle	Comparator regimen and combination agent
5-FU**	800 mg/m 	Q3W	IV infusion	Continuous Days 1-5 (120 hours) of each cycle	Comparator regimen and combination agent
Capecitabine**	1000 mg/m  BID	Q3W	Oral	D1-14	Comparator regimen and combination agent

* Duration of cisplatin treatment may be capped at 6 cycles as per local country guidelines, however treatment with 5-FU/capecitabine may continue per protocol.
 
**Although use of 5-FU infusion is preferred, capecitabine 1000 mg/m^2 bid D1-14 Q3W may be permitted according to local guideline. Investigator decision regarding the type of comparator used (5-FU or capecitabine) should be determined prior to randomization in the trial.
					

All trial treatments will be administered on an out-patient basis.

Trial treatment should begin on the day of randomization or as close as possible to the date on which the subject is allocated/assigned.

All supplies indicated in [Table 3](#) above will be provided centrally by the Sponsor or locally by the trial site, subsidiary or designee, depending on local country operational or regulatory requirements.

For any commercially available product that is provided by the trial site, subsidiary or designee every attempt will be made to source these supplies from a single lot/batch number. The trial site will be responsible for recording the lot number, manufacturer and expiry date of any locally purchased product.

The investigator shall take responsibility for and shall take all steps to maintain appropriate records and ensure appropriate supply, storage, handling, distribution and usage of trial treatments in accordance with the protocol and any applicable laws and regulations.

## **5.2.1 Dose Selection/Modification**

### **5.2.1.1 Dose Selection (Preparation)**

The rationale for selection of dose of pembrolizumab to be used in this trial is provided in Section 4.0– Background & Rationale. Details on preparation and administration of pembrolizumab are provided in the Pharmacy Manual.

Preparation of cisplatin, 5-FU and capecitabine should follow the local product label. The body surface area (BSA) in m^2 should be calculated per local guidance.

### **5.2.1.2 Dose Modification**

If appropriate, the Investigator may attribute each toxicity event to cisplatin, 5-FU (or capecitabine) or pembrolizumab alone in the combination arms and use a stepwise dose reduction according to [Table 4](#) to [Table 8](#). For individual subjects requiring a dose modification, treatment for each new cycle may be delayed if the scheduled off-drug periods are not adequate to allow for recovery to Grade  $\leq 1$  or the baseline status of the subject.

Pembrolizumab/placebo dose reductions are not permitted. Pembrolizumab/placebo treatment may be interrupted or discontinued due to toxicity. If a dose reduction for toxicity occurs with any agent, the dose may not be re-escalated. Subjects can have a maximum of 2 dose modifications (if applicable) to each of the components of study therapy throughout the course of the study for toxicities. If a subject experiences several toxicities and there are conflicting recommendations, please follow the most conservative dose adjustment recommended (dose reduction appropriate to the most severe toxicity). Subjects who require a 3rd dose modification to any particular component will have that agent discontinued.

Reduction of one chemotherapy agent and not the other agent is appropriate if, in the opinion of the Investigator, the toxicity is clearly related to one of the treatments. If, in the opinion of the Investigator, the toxicity is related to the combination of both chemotherapy agents, both drugs should be reduced according to recommended dose modifications. If the toxicity is related to the combination of three agents, chemotherapy should be reduced, interrupted or discontinued; pembrolizumab/placebo should be interrupted or discontinued according to the recommended dose modifications. If a decision is made to discontinue combination chemotherapy due to treatment related AE(s), the subject can be unblinded after discussion with sponsor to identify study treatment. Subjects receiving pembrolizumab therapy may have both the cisplatin and 5-FU or capecitabine discontinued and continue on pembrolizumab alone, while subjects on combination with placebo (arm 3) may discontinue from study treatment.

The Common Terminology Criteria for Adverse Events version 4.0 (CTCAE 4.0) must be used to grade the severity of AEs. All dose modifications should be based on the AE requiring the greatest dose modification. Dose modifications are detailed in [Table 4](#) through [Table 8](#). Exceptional circumstances to following the dose modification tables below may be considered after consultation with the Sponsor.

Table 4 Dose Modifications for Trial Medications

	Dose level 0	Dose level -1	Dose level -2	Dose level -3
Cisplatin	80 mg/m 	60 mg/ m 	40 mg/ m 	Discontinue
5-FU Capecitabine	800 mg/ m  1000mg/ m  BID	600 mg/ m  750mg/ m  BID	400 mg/ m  500mg/ m  BID	Discontinue
Pembrolizumab/placebo	200 mg fixed dose	Dose reductions are not permitted	Dose reductions are not permitted	Dose reductions are not permitted

If a toxicity is not otherwise specified, investigators should refer to the label or local guidelines for cisplatin and 5-FU, (or capecitabine) for dose adjustments.

#### 5.2.1.2.1 Dose Modification and Toxicity Management Guidelines for Pembrolizumab/Placebo

##### **Dose modification and toxicity management for immune-related AEs associated with pembrolizumab**

Adverse events associated with pembrolizumab exposure may represent an immunologic aetiology. These immune-related AEs (irAEs) may occur shortly after the first dose or several months after the last dose of pembrolizumab treatment and may affect more than one body system simultaneously. Therefore, early recognition and initiation of treatment is critical to reduce complications. Based on existing clinical trial data, most irAEs were reversible and could be managed with interruptions of pembrolizumab, administration of corticosteroids and/or other supportive care. For suspected irAEs, ensure adequate evaluation to confirm aetiology or exclude other causes. Additional procedures or tests such as bronchoscopy, endoscopy, skin biopsy may be included as part of the evaluation. Based on the severity of irAEs, withhold or permanently discontinue pembrolizumab and administer corticosteroids. Dose modification and toxicity management guidelines, for irAEs associated with pembrolizumab are provided in [Table 5](#).

Table 5 Dose Modification and Toxicity Management Guidelines for Immune-related AEs Associated With pembrolizumab

General instructions:				

 
1. Corticosteroid taper should be initiated upon AE improving to Grade 1 or less and continue to taper over at least 4 weeks.
 
2. For situations where pembrolizumab has been withheld, pembrolizumab can be resumed after AE has been reduced to Grade 1 or 0 and corticosteroid has been tapered. Pembrolizumab should be permanently discontinued if AE does not resolve within 12 weeks of last dose or corticosteroids cannot be reduced to <math>\leq 10</math> mg prednisone or equivalent per day within 12 weeks.
 
3. For severe and life-threatening irAEs, IV corticosteroid should be initiated first followed by oral steroid. Other immunosuppressive treatment should be initiated if irAEs cannot be controlled by corticosteroids.
 
				
Immune-related AEs	Toxicity grade or conditions (CTCAEv4.0)	Action taken to pembrolizumab	irAE management with corticosteroid and/or other therapies	Monitor and follow-up
Pneumonitis	Grade 2	Withhold	
 
• Administer corticosteroids (initial dose of 1-2 mg/kg prednisone or equivalent) followed by taper
 
	
 
• Monitor subjects for signs and symptoms of pneumonitis
 
• Evaluate subjects with suspected pneumonitis with radiographic imaging and initiate corticosteroid treatment
 
• Add prophylactic antibiotics for opportunistic infections
 

	Grade 3 or 4, or recurrent Grade 2	Permanently discontinue	
 
•
 
	
Diarrhoea / Colitis	Grade 2 or 3	Withhold	
 
• Administer corticosteroids (initial dose of 1-2 mg/kg prednisone or equivalent) followed by taper
 
	
 
• Monitor subjects for signs and symptoms of enterocolitis (ie, diarrhoea, abdominal pain, blood or mucus in stool with or without fever) and of bowel perforation (ie, peritoneal signs and ileus).
 
• Subjects with <math>\geq</math> Grade 2 diarrhoea suspecting colitis should consider GI consultation and performing endoscopy to rule out colitis.
 
• Subjects with diarrhoea/colitis should be advised to drink liberal quantities of clear fluids. If sufficient oral fluid intake is not feasible, fluid and electrolytes should be substituted via IV infusion.
 

	Grade 4	Permanently discontinue		

Immune-related AEs	Toxicity grade or conditions (CTCAEv4.0)	Action taken to pembrolizumab	irAE management with corticosteroid and/or other therapies	Monitor and follow-up
AST / ALT elevation or Increased bilirubin	Grade 2	Withhold	
 
Administer corticosteroids (initial dose of 0.5- 1 mg/kg prednisone or equivalent) followed by taper
 
	
 
Monitor with liver function tests (consider weekly or more frequently until liver enzyme value returned to baseline or is stable)
 

	Grade 3 or 4	Permanently discontinue	
 
Administer corticosteroids (initial dose of 1-2 mg/kg prednisone or equivalent) followed by taper
 
	
Type 1 diabetes mellitus (T1DM) or Hyperglycaemia	Newly onset T1DM or Grade 3 or 4 hyperglycaemia associated with evidence of $\beta$ -cell failure	Withhold	
 
Initiate insulin replacement therapy for subjects with T1DM
 
Administer anti-hyperglycaemic in subjects with hyperglycaemia
 
	
 
Monitor subjects for hyperglycaemia or other signs and symptoms of diabetes.
 

Hypophysitis	Grade 2	Withhold	
 
Administer corticosteroids and initiate hormonal replacements as clinically indicated.
 
	
 
Monitor for signs and symptoms of hypophysitis (including hypopituitarism and adrenal insufficiency)
 

	Grade 3 or 4	Withhold or permanently discontinue 		
Hyperthyroidism	Grade 2	Continue	
 
Treat with non-selective beta-blockers (eg, propranolol) or thionamides as appropriate
 
	
 
Monitor for signs and symptoms of thyroid disorders.
 

	Grade 3 or 4	Withhold or permanently discontinue 		
Hypothyroidism	Grade 2-4	Continue	
 
Initiate thyroid replacement hormones (eg, levothyroxine or liothyronine) per standard of care
 
	
 
Monitor for signs and symptoms of thyroid disorders.
 

Nephritis and Renal dysfunction	Grade 2	Withhold	
 
Administer corticosteroids (prednisone 1-2 mg/kg or equivalent) followed by taper.
 
	
 
Monitor changes of renal function
 

	Grade 3 or 4	Permanently discontinue		

Immune-related AEs	Toxicity grade or conditions (CTCAEv4.0)	Action taken to pembrolizumab	irAE management with corticosteroid and/or other therapies	Monitor and follow-up
Myocarditis	Grade 1 or 2	Withhold	
 
Based on severity of AE administer corticosteroids
 
	
 
Ensure adequate evaluation to confirm aetiology and/or exclude other causes
 

	Grade 3 or 4	Permanently discontinue		
All other immune-related AEs	Intolerable/persistent Grade 2	Withhold	
 
Based on type and severity of AE administer corticosteroids
 
	
 
Ensure adequate evaluation to confirm aetiology and/or exclude other causes
 

	Grade 3	Withhold or discontinue based on the type of event. Events that require discontinuation include and not limited to: Guillain-Barre Syndrome, encephalitis		
	Grade 4 or recurrent Grade 3	Permanently discontinue		

1. Withhold or permanently discontinue pembrolizumab is at the discretion of the investigator or treating physician.
 
NOTE:                      For subjects with Grade 3 or 4 immune-related endocrinopathy where withhold of pembrolizumab is required, pembrolizumab may be resumed when AE resolves to <math>\leq</math> Grade 2 and is controlled with hormonal replacement therapy or achieved metabolic control (in case of T1DM).
				

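### Table 5 does not say whether myocarditis that improves from Grade 2 to Grade 1 may resume pembrolizumab, although its own row withholds at Grade 1

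*Combined protocol and SAP*

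**What the plan says.** Table 5 in protocol Section 5.2.1.2.1 opens with general instructions for all immune-related events and then lists the events row by row.

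- General instruction 1 covers steroid withdrawal: "Corticosteroid taper should be initiated upon AE improving to Grade 1 or less and continue to taper over at least 4 weeks".
- General instruction 2 covers every case in which the drug has been withheld: "pembrolizumab can be resumed after AE has been reduced to Grade 1 or 0 and corticosteroid has been tapered". It makes no exception by event. It also sets a time limit: "Pembrolizumab should be permanently discontinued if AE does not resolve within 12 weeks of last dose".
- The myocarditis row withholds at Grade 1 or 2 and stops permanently at Grade 3 or 4. Its management column reads "Based on severity of AE administer corticosteroids", and its follow-up column asks for an adequate work-up of the cause. The row gives no resume grade of its own.

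Section 5.2.1.2 adds a general line for new cycles: "treatment for each new cycle may be delayed if the scheduled off-drug periods are not adequate to allow for recovery to Grade" 1 or less, or the subject's baseline. It too makes no exception for myocarditis.

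**The concern.** The sponsor set a lower threshold for holding the drug in myocarditis than in any other graded row of Table 5, but left the shared resume rule as it was. A Grade 2 myocarditis that has settled to Grade 1, with steroids tapered, meets the resume rule while still at a grade the row holds. Two sites can follow the same table and manage the same subject differently, and one of them would give the next dose with the event still present.

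What is at stake is subject safety in a rare situation. The row stops treatment for good at Grade 3 or 4 and holds it even at Grade 1, so the sponsor evidently wanted extra caution for this event.

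**Working it through.** The check is textual: compare the resume grades with the hold grades row by row, then look for any sentence that ranks the two.

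**Step 1. Overlap of hold and resume grades.** General instruction 2 gives the resume grades {0, 1}. The hold grades come from the rows of Table 5.

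| Row | Grades that can lead to a hold | Overlap with {0, 1} |
|---|---|---|
| Pneumonitis | 2 | none |
| Diarrhoea/colitis | 2, 3 | none |
| AST/ALT or bilirubin | 2 | none |
| Type 1 diabetes/hyperglycaemia | new-onset diabetes (no grade named); hyperglycaemia 3, 4 | none named |
| Hypophysitis | 2; 3, 4 (hold or stop) | none |
| Hyperthyroidism | 3, 4 (hold or stop) | none |
| Hypothyroidism | never held | not applicable |
| Nephritis/renal | 2 | none |
| Myocarditis | 1, 2 | **1** |
| All other | intolerable or persistent 2; 3 (hold or stop) | none |

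There are ten rows, and nine can withhold. One of the nine overlaps: {0, 1} ∩ {1, 2} = {1}.

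**Step 2. What a literal reading gives.** An event that peaked at Grade 2 satisfies instruction 2 on reaching Grade 1. An event first seen at Grade 1 can only be reduced to Grade 0. On that reading, the Grade 1 hold rests entirely on the word *reduced*, and the milder event faces the stricter resume grade.

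**Step 3. Does other text settle it?**

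- Section 5.2.1.2 has two tie-breaks. "If a subject experiences several toxicities and there are conflicting recommendations, please follow the most conservative dose adjustment recommended" applies to a subject with more than one toxicity. "All dose modifications should be based on the AE requiring the greatest dose modification" chooses between adverse events. Neither ranks two instructions that apply to one event.
- "Exceptional circumstances to following the dose modification tables below may be considered after consultation with the Sponsor" covers departures from the tables. A site acting on general instruction 2 is following the table, so this does not say which line governs.
- The closing note of Table 5 gives a separate resume threshold, but only for Grade 3 or 4 endocrinopathy. Footnote 1, on investigator discretion, is attached only to hypophysitis and hyperthyroidism.
- Section 5.6.1 has seven immune-related headings (pneumonitis, diarrhoea/colitis, diabetes/hyperglycaemia, hypophysitis, thyroid, hepatic, renal) plus infusion reactions. None is myocarditis, and the section refers back to Table 5.
- The 12-week limit turns on whether the event resolves, and Table 5 does not define that as Grade 0. Tables 7 and 8, for the chemotherapy agents, count Grade 0-1 as resolved.

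No text states the order of precedence.

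**The case against.** The best defence is that the two lines govern different moments. The row tells the site what to do when myocarditis appears, and instruction 2 tells it what may follow once the drug has been held. A treated event that has come down to Grade 1 is not the same as a new, untreated Grade 1 event, so holding the second and allowing the first is coherent. Alternatively, a careful site would let the specific row govern over the general instruction, which keeps Grade 1 on hold. Both readings are possible, but they lead to opposite actions and the protocol states neither. Where the table's authors wanted a different resume threshold, for severe endocrinopathy, they wrote it down.

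The limits on the point are fair and they stand. Instruction 2 permits resumption and does not require it. Where steroids are given, the taper of at least four weeks starts only at Grade 1 or less. The Sponsor can be consulted, and Section 5.8.1 requires stopping for unacceptable adverse experiences.

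A reader might infer that persistent Grade 1 myocarditis would go unseen, because the only scheduled ECG is at screening and Table 10 lists no cardiac marker. The documents do not support that. Section 7.1 provides for unscheduled procedures and extra safety testing, Section 5.2.1.2.1 calls for adequate evaluation of suspected immune-related events, and Section 7.1.3.1 requires laboratory review before each dose and follow-up of drug-related abnormal values until they resolve. None of these makes Grade 0 a condition of re-dosing, but they answer the claim that nothing would detect it.

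**Conclusion.** The ambiguity is real and confined to one of the nine rows that can withhold. One available reading of Table 5 permits pembrolizumab to be resumed at a myocarditis grade the table itself holds, and nothing in the protocol rules that reading out. This rests only on the wording of Table 5 and on no other section supplying a ranking.

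The size in subjects cannot be given, because the documents contain no myocarditis incidence; few are likely to be affected. Alpha, power and endpoints are unchanged.

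Two stronger readings should be set aside. The protocol does not direct sites to re-dose at Grade 1, because the instruction is permissive. Nor can the 12-week stop be used to put an upper limit on the extra hold that a Grade 0 rule would bring. That would need resolution to mean Grade 0, which Table 5 does not say, and Section 7.1.1.9 provides for interruptions beyond 12 weeks after consultation with the Sponsor.

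**What to change.** Add one line to the myocarditis row of Table 5: *may resume only after resolution to Grade 0 with corticosteroids tapered; this overrides general instruction 2*. Grade 0 is the conservative choice that matches the row's own hold at Grade 1. The final threshold is a clinical decision for the sponsor, and one wanting something stricter could state permanent discontinuation instead.

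The cost is one table line and a clarification letter to sites. The downside is that a few subjects whose myocarditis persists at Grade 1 would be held longer or stopped. No change to sample size or analysis follows.
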